### 3.2 RET MUTATION ANALYSIS PROCEDURE

The assay to determine mutation status will be done or may have been done (in case of retrospective patients) in certified laboratories and must be based on one of these 3 tests:

- Sequencing
- PCR including ARMS methodology
- Comparative genomic hybridization (CGH)

For this study, the criteria for definition of the RET status is as follows:

- If mutation is present in M918T (exon 16) or any other additional exon tested where RET mutations have been described (10, 11, 13 to 16), then the patient is RET mutation positive.
- If mutation is absent in M918T (exon 16), and in any of the other additional exons where RET mutations have been described (10, 11, 13 to 16), then the patient is RET mutation negative.

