# 1 INTRODUCTION

## 1.1 BACKGROUND

In Study D4200C00058 (the pivotal clinical trial in which the efficacy and safety of vandetanib 300 mg were compared to placebo in patients with medullary thyroid cancer (MTC), Rearranged During Transfection (RET) mutation testing was performed by performing a polymerase chain reaction (PCR)-based assay called the Amplification Refractory Mutation System (ARMS) assay to detect the most common mutation in sporadic MTC (the M918T mutation) and by sequencing the 6 most commonly mutated exons in RET (10, 11, 13, 14, 15, and 16). A tumor was considered to have a RET mutation if it either had an M918T mutation by the ARMS assay, or a RET mutation in any of exons 10, 11, 13 to 16. A RET mutation negative tumor was defined as having no M918T mutation by ARMS and a wild-type RET sequence in each of exons 10, 11, 13 to 16. The mutation status was considered to be unknown in tumors where an assay failed to yield a sequence at any of the tested exons (by sequencing or ARMS assay), and none of the successful assays demonstrated a mutation.

Therefore, the criteria for defining a patient as RET mutation negative were very stringent - all 7 assays had to have been successful and demonstrated no mutation. Conversely, only one assay had to demonstrate a RET mutation for the patient to be considered RET mutation positive. Because many of the tumor samples were in poor condition and the stringent criteria for defining patients as RET mutation negative, a high percentage of patients had an unknown RET mutation status and only a small percentage of patients were identified as RET mutation negative.

The mutation status outcome in Study D4200C00058 (N=331) was as follows:

- 57% of patients were defined as RET mutation positive
- 41% had an unknown RET mutation status
- 2% (8) patients were identified as being RET mutation negative based on the protocol definition for RET mutation status.

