To better define the efficacy of vandetanib 300 mg in patients who were RET mutation negative, a post-hoc subgroup analysis of RET mutation negative status based on absence of M918T mutation of the pivotal Study D4200C00058 was performed. Based on a recent study with a data base consisting of 100 sporadic MTC tumors whose complete exon sequencing was done at all 6 RET exons where RET mutations have been described (1), it is estimated that if a patient does not have the M918T mutation, there is an 86% likelihood that the patient will not have a RET mutation at all; this is also supported by other studies (2). In Study D4200C00058, it was also established that 86% of patients without an M918T mutation had no other RET mutation identified (79 sporadic patients were identified without a M918T mutation and no RET mutation identified at any of the other 6 exons tested in 71 of these patients) (3).

Thus, patients with the sporadic form of MTC without the M918T mutation have nearly a 90% probability of being RET mutation negative. Table 3 summarizes the results of the post hoc analysis of efficacy endpoints in patients with a documented RET mutation and patients who were M918T mutation negative and other mutations not tested or negative.

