#### *Disease characteristics*

- First diagnosis of sporadic MTC date
- Date of diagnosis of sporadic, unresectable, locally advanced/metastatic MTC
- Investigator's assessment of symptomatic and aggressive (clinical deterioration, calcitonin [CTN], carcinoembryonic antigen [CEA] doubling time, change of tumor volume, other)

- Date of last determination of disease progression
- RET determination (if more than 1 determination has been done, information from all will be collected):
  - Date of RET assay
  - Mutational status
  - Assay type
  - Tissue type used for assay
  - Date of tissue biopsy
  - Exons analyzed
- Disease assessment (including number/sites of disease locations): at baseline (for all patients and before treatment with vandetanib for the patients who received vandetanib) and at follow-up visits for prospective patients or at any time point for retrospective patients (whenever performed)
- Date of measurements
- Symptoms at baseline (before treatment with vandetanib for the patients who received vandetanib) and at every disease assessment time point (lump at the base of the neck, dysphagia, respiratory difficulty, hoarseness, diarrhea, weight loss, lethargy, asthenia, anorexia and bone pain)
- CTN and CEA doubling time at baseline
- CTN and CEA at every disease assessment time point

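### Section 3.2 does not clearly require a successful wild-type result in every listed exon before a patient is called RET mutation negative, so partly tested patients can enter that group

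*Protocol*

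**What the plan says.** Protocol Section 3.2 says the assay "must be based on one of these 3 tests": sequencing, PCR including ARMS methodology, or comparative genomic hybridization. It then gives two rules.

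- Positive: "If mutation is present in M918T (exon 16) or any other additional exon tested where RET mutations have been described".
- Negative: "If mutation is absent in M918T (exon 16), and in any of the other additional exons where RET mutations have been described".

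Both rules give the same list of exons: 10, 11 and 13 to 16. There is no third class, and no rule for an exon that failed or was not tested. Section 4.2 requires a known and definite RET status, but defines it by reference to Section 3.2.

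Section 1.1 describes how Study D4200C00058 did this. It used an "Amplification Refractory Mutation System (ARMS) assay to detect the most common mutation in sporadic MTC (the M918T mutation") and sequenced six exons. For a negative result, "all 7 assays had to have been successful and demonstrated no mutation". A tumour with any failed exon and no mutation found was classed as unknown. Section 1.1 attributes the small number of negatives to this strict rule together with poor samples.

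Sections 13.2 and 13.3 plan 20 to 25 RET-negative patients on vandetanib. They pool prospective patients, retrospective patients and re-analysed Study D4200C00058 patients, and also report each source separately. Section 8.2 collects "Exons analyzed" for every RET determination.

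**The concern.** The study has to confirm benefit in RET-negative patients, so the rule that admits a patient to that group is the most important definition in the protocol. If a chart patient with an M918T test alone, or M918T plus one exon, can be called negative, some RET-positive patients will sit in the RET-negative group. They would raise its response rate and narrow the contrast with the RET-positive group. A larger sample does not remove that bias.

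The exposure is practical. The amendment rationale reports 8 RET-negative patients enrolled by August 2018 and no new prospective patient after June 2017. If none were added prospectively, reaching 20 to 25 needs at least 12 to 17 chart patients (12/20 = 60% to 17/25 = 68%), whose tests were chosen locally in the past.

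**Working it through.** **Wording, side by side.** For Study D4200C00058, Section 1.1 asks for wild type in each listed exon, requires all seven assays to succeed, and calls the rest unknown. Section 3.2 has none of these three elements. Its negative rule can be read in two ways:

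- Reading A: absent in all the listed exons, so all must have been read.
- Reading B: absent in M918T and in whichever other exons were tested.

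Reading A fits the listed exons. Reading B fits the acceptance of a single technique such as ARMS, and the positive rule, which speaks of additional exons tested. The section does not decide between them.

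**Inputs.**

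- Probability of no RET mutation given no M918T: Section 1.1, "there is an 86% likelihood that the patient will not have a RET mutation at all". So the misclassified share is m = 1 − 0.86 = 0.14 if only M918T is read.
- ORR in documented RET-positive patients: 52% (Table 3).
- Planned RET-negative sample: 20 to 25 (Section 13.2).
- Planning ORR 35%, SD 0.4770 (Section 13.2, Table 1).

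**The plan's own figure.** The interval is 35% ± 1.96 × 47.70/√n, with SD = √(0.35 × 0.65) = 0.4770.

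- n = 20: ± 20.9, giving 14.1% to 55.9%
- n = 25: ± 18.7, giving 16.3% to 53.7%
- n = 30: ± 17.1, giving 17.9% to 52.1%

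All three match Table 1.

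**Misclassified patients, upper bound.**

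- Expected number: 20 × 0.14 = 2.8; 25 × 0.14 = 3.5.
- Chance of at least one: 1 − 0.86^20 = 95%; 1 − 0.86^25 = 98%.

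**Effect on the RET-negative ORR.** For a true ORR x, the observed ORR is 0.86x + 0.14 × 0.52, so the inflation is 0.14 × (0.52 − x).

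| True ORR | Observed | Inflation, m = 0.14 | Inflation, m = 0.10 |
|---|---|---|---|
| 0% | 7.3% | 7.3 points | 5.2 points |
| 10% | 15.9% | 5.9 points | 4.2 points |
| 20% | 24.5% | 4.5 points | 3.2 points |
| 35% | 37.4% | 2.4 points | 1.7 points |

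The m = 0.10 column uses the figure of nearly 90% that Section 1.1 also gives. In reverse, an observed 35% at m = 0.14 implies a true ORR of (0.35 − 0.0728)/0.86 = 32.2%. The contrast with the RET-positive group becomes 0.86 × (0.52 − x), that is, 86% of its true size.

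**How firm is the 86%?** Section 1.1 also supports it with 71 of 79 Study D4200C00058 patients, but 71/79 = 89.9%. The SmPC in Appendix B (Section 5.1) describes 71 of these 79 as incompletely sequenced, and says that mutations on other exons cannot be excluded. The two statements about the 71 conflict, so this count does not firmly support either 86% or 90%.

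**The case against.** The best defence is linguistic. After a word such as absent, any usually means all, and the negative rule lists the exons and omits the word tested that the positive rule contains. On that reading an ARMS-only patient does not qualify. The list of three tests then restricts technique and says nothing about completeness. PCR is also wider than ARMS. The demand for a definite status in Section 4.2 would exclude unknowns, so no third class would be needed. This is a fair reading, and it stops anyone from saying that the protocol plainly admits ARMS-only patients. It does not remove the problem, because Section 4.2 refers back to the same ambiguous sentence and a failed exon is still not classified.

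RET results are also verified against source records (Section 11.1), and negative status is verified for retrospective patients (Section 7.1). That confirms what was reported, not how many exons make a negative. A sensitivity analysis by completeness could sit in a SAP that is not shown, but the class definition sits in the protocol.

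The size argument stands. The computed shift is a worst case, and at 35% it is about a tenth of the half-width of the interval.

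**Conclusion.** The protocol does not clearly require complete exon testing for a RET-negative label. Partly tested patients can enter the group; how many will do so depends on the tests that sites used. At most, 2.8 of 20 or 3.5 of 25 patients would be misclassified and the ORR inflated by 2.4 to 7.3 points for a true ORR between 35% and 0%. This assumes M918T-only testing throughout, 14% with other mutations, and that the 52% ORR applies to patients with non-M918T mutations, which the documents do not show. Partial sequencing would give less. The shift is small beside an interval of about ± 19 to 21 points at 35%, but it favours the drug whenever the true RET-negative ORR is below 52%.

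Two stronger inferences are tempting and unsupported. A reader might infer that the regulator found the earlier data insufficient because of incomplete testing. The answer quoted in the amendment rationale calls the data insufficient for the RET-negative population, immature and limited, and mentions slow recruitment; it does not name exon testing. A reader might also infer that the pooled RET-negative column does mix two definitions. The rule used to re-analyse the Study D4200C00058 samples is not stated, so this is only a risk, and reporting by source group would partly expose it.

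**What to change.** In Section 3.2, define fully tested RET negative as no M918T and a successful wild-type result in each of exons 10, 11, 13, 14, 15 and 16. Class a patient with any untested or failed exon and no mutation found as incompletely tested, no mutation found. State that the same rule applies to prospective, retrospective and re-analysed Study D4200C00058 patients.

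Report RET-negative ORR, DCR and PFS twice: for the fully tested set, and for fully and incompletely tested patients together. Use the exon field already collected under Section 8.2.

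The change is to wording and tables; it needs no new data item and discards no patient. The cost is precision. The strict rule gave 8 negatives of 331 (2.4%) in Study D4200C00058, partly because samples were poor, so the fully tested set here may fall below 20 to 25 and its interval will be wider. The report should state the size and precision actually achieved for that set.

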## 4 SELECTION OF PATIENT POPULATION

### 4.1 INVESTIGATORS

Investigators experienced in the treatment of symptomatic, aggressive, sporadic, unresectable, locally advanced/metastatic MTC and based in European Union (EU) countries where vandetanib is approved and available for use in the treatment of MTC.

### 4.2 INCLUSION CRITERIA

The patient population that will be included in the NIS must fulfill all the following criteria:

- I 01. Signed informed consent for prospective patients. No need for signed informed consent for retrospective patients (waiver).
- I 02. Male or female aged 18 years or above for prospective patients. No age restriction for retrospective patients.
- I 03. Histological diagnosis of MTC (for retrospective patients [prevalent MTC patients] diagnosis could be as early as possible, without any limitation for the date of diagnosis).
- I 04. Patients with symptomatic and aggressive sporadic MTC, who have unresectable, locally advanced/metastatic disease. (The factors considered by the Investigator to determine a patient's disease to be symptomatic and aggressive will be recorded in the electronic case report form [eCRF], allowing for missing data for the retrospective patients).
- I 05. Measurable disease:
  - Assessment confirmed within the 12 weeks previous to start of treatment, and
  - Defined according to RECIST 1.1: at least 1 lesion, not irradiated, that can be accurately measured as  $\geq 10$  mm in the longest diameter (except lymph nodes which must have short axis  $\geq 15$  mm) with computed tomography (CT) or magnetic resonance imaging (MRI) and which is suitable for accurate repeated measurements. Measurable lesions with calcifications should not be assessed as target lesions unless no other measurable lesion is available.

Known definite RET mutation status (definition according to [Section 3.2](#)). The status should be:

- For prospective patients prescribed with vandetanib: positive or negative.
- For prospective patients not prescribed with vandetanib: negative.
- For retrospective patients prescribed or not prescribed with vandetanib: negative.

- For prospective patients: RET mutation status must be determined from a tumor sample obtained within 18 months prior to enrollment. It is strongly recommended that a tissue sample obtained within 6 months prior to enrollment is used. For retrospective patients: RET mutation negative mutation status could have been determined within 18 months before or after start of treatment (with vandetanib or another drug). In case of retrospective patient treated with another drug, the patient should have been treated with vandetanib at any time.
- I 06. For prospective patients newly prescribed vandetanib 300 mg, the prescription should be issued according to marketing authorization and following the vandetanib SmPC ([Appendix B](#)). The starting dose could be reduced to 200 mg in patients with moderate renal impairment. For retrospective patients, the prescription may or may not have been issued according to the SmPC.
- I 07. Note: The **prescription of the medicinal product is clearly separated from the decision to include the patient** in the NIS. The study is observational, meaning that vandetanib treatment initiation should never be delayed in order to meet any inclusion criteria of the study.

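### Section 4.2 requires a tumor sample for RET status in prospective patients but names no specimen for retrospective ones, so a negative non-tumor result could qualify a patient as RET mutation negative

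*Protocol*

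**What the plan says.** For prospective patients, section 4.2 is explicit: "For prospective patients: RET mutation status must be determined from a tumor sample obtained within 18 months prior to enrollment". For retrospective patients the same criterion gives only the timing of the determination: "For retrospective patients: RET mutation negative mutation status could have been determined within 18 months before or after start of treatment". It names no material.

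Section 4.2 refers to section 3.2 for the definition of status. There the assay must come from a certified laboratory and "must be based on one of these 3 tests" (sequencing, PCR including ARMS, or CGH). A patient is negative on this condition: "If mutation is absent in M918T (exon 16), and in any of the other additional exons where RET mutations have been described". Technique and exons are fixed; the specimen is not.

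Section 7.1 asks the investigator to verify negative status in retrospective patients, without saying on what material. It also says that all RET-negative patients found in the record search should be included, unless a contract for another company's trial prevents it. Section 8.2 collects "Tissue type used for assay" and the date of tissue biopsy, but no eligibility or classification rule uses either item. Section 11.1 has the RET result checked against the medical record, and does not mention the specimen.

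The population is defined as "Patients with symptomatic and aggressive sporadic MTC, who have unresectable, locally advanced/metastatic disease". Retrospective patients may enter only with negative status.

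**The concern.** In sporadic disease the protocol itself treats RET status as a property of the tumor. Section 1.1 describes how the pivotal study, D4200C00058, classified the tumor, and it relies on a database of 100 sporadic tumors. The reference list cites a 10-year follow-up study of somatic RET mutations in sporadic disease. A negative result from other material does not show that the tumor is negative.

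The retrospective cohort was added to supply RET-negative patients for the regulator's specific obligation. Because these patients can enter only as negative, a wrong classification runs one way, into the group that the obligation concerns. If RET-mutated patients respond more often, the RET-negative ORR is overstated and the RET contrast understated. Section 13.3 also rests pooling on selection criteria meant to make the cohorts comparable. A tumor rule in one cohort and none in the other weakens that premise.

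**Working it through.** **Is the gap closed elsewhere?** Sections 3.2, 7.1, 8.2 and 11.1 set no specimen condition for an existing retrospective result. The biopsy wording in 7.1 concerns tests run to confirm eligibility. The advice on tissue samples in Appendix B (SmPC section 4.4) is a recommendation. The gap stands.

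**The plan's own figure.** Table 1 uses 35% ± 1.96 × 0.4770/√n.
- n = 20: ± 20.9 points, giving 14.1-55.9%.
- n = 25: ± 18.7 points, giving 16.3-53.7%.

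Both match the table. No stated figure is in dispute.

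**Inputs for an illustration**
- ORR in the vandetanib arm: 52% with a documented mutation (n = 187), 35% with no M918T mutation and other mutations not tested or negative (n = 79) (Table 3).
- 331 patients in the pivotal study (section 1.1), 298 of them sporadic (Appendix B, SmPC section 5.1), so 331 − 298 = 33 not sporadic.
- 8 prospective RET-negative patients enrolled (amendment rationale); target 20 to 25 (section 13.2).

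**Assumed share of non-tumor negatives with a tumor mutation.** Take all 33 non-sporadic patients as RET positive, which leaves 187 − 33 = 154 sporadic positives.
- Over all sporadic patients: 154/298 = 51.7%.
- Over those positive or without M918T: 154/(154 + 79) = 66.1%. The 79 are not a clean negative group, because Appendix B reports incomplete sequencing in 71 of them.

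**Largest possible non-tumor share.** The 8 prospective negatives fall under the tumor rule. If all 8 count towards the target and the rest are retrospective, these number 20 − 8 = 12 or 25 − 8 = 17, that is 12/20 = 60% or 17/25 = 68%.

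**Expected RET-negative ORR.** With f the fraction of retrospective patients qualified on non-tumor material only, the misclassified share is m = f × (0.60 or 0.68) × (0.517 or 0.661), and ORR = 35 + 17m.

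| f | m | ORR read as |
|---|---|---|
| 0.25 | 0.078 to 0.112 | 36.3 to 36.9% |
| 0.50 | 0.155 to 0.225 | 37.6 to 38.8% |
| 1.00 | 0.310 to 0.449 | 40.3 to 42.6% |

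At f = 1 the gap to 52% narrows from 17 points to 52 − 40.3 = 11.7 down to 52 − 42.6 = 9.4 points.

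**Sensitivity to the baseline.** If the true RET-negative ORR were 20% (an assumption), f = 1 gives 20 + 32m = 29.9 to 34.4%, close to the 35% planning value.

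**The case against.** The strongest reply is that the intent is clear. RET is handled as a tumor property throughout, status must be known and definite, and retrospective negatives must be verified. The collected items include a biopsy date, which a result from non-tumor material could not supply. The RET rules never mention blood or germline testing. Analyses are to be shown by cohort as well as pooled (section 13.3, Table 2), so the tumor-tested prospective negatives stay visible. Re-analysed patients from the pivotal study, classified on archived tumor, would dilute the effect in the pooled column. The shift at f = 0.25 to 0.50 is 1 to 4 points, against half-widths of 19 to 21 points.

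Most of this stands as mitigation. It makes non-tumor results identifiable, but it does not make them ineligible, and section 7.1 tells sites to include every RET-negative patient they find. The shift is also systematic, so more patients would not remove it.

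A reader might infer that blood tests were in fact accepted, or that the RET-negative ORR could read 44-46%. The documents support neither. Nothing shows which specimens were used. And 44-46% (35 + 17 × 0.517 or 0.661) needs every patient in the group to be qualified on non-tumor material. That could describe at most the retrospective column alone, since 8 patients fall under the tumor rule.

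**Conclusion.** The asymmetry in section 4.2 is explicit, and no other section repairs it for retrospective patients. The direction of error is fixed: it can only add tumor-positive patients to the RET-negative group. Its size is unknown. About 40-43% instead of 35% is the illustrated upper end, with every retrospective result non-tumor; about 36-39% applies if a quarter to a half are.

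These figures assume that all 8 prospective negatives count towards the target, that 52-66% of non-tumor negatives carry a tumor mutation, that misclassified patients respond at 52%, and that 35% is the true RET-negative rate. The last is doubtful, given the incomplete sequencing behind it. The route through non-tumor material is an inference from what the text leaves open. It does not show that the cohort is contaminated. The rule still needs correcting, because RET status defines the study's central groups.

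**What to change.** - In 4.2, state that RET-negative status in retrospective patients must also have been determined from tumor tissue.
- In 3.2, state that a negative result from non-tumor material alone does not establish RET-negative status.
- Use the collected tissue type and biopsy date to enforce both.
- Class patients with only a non-tumor result as RET unknown, leave them out of the RET-negative estimates and the count of 20 to 25, and list them separately.

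If archived tumor is to be tested to recover such patients, the 18-month window for retrospective patients in 4.2 must be reworded too, for example by applying it to the date of the tissue sample, as the prospective rule does. If the window limits the assay date on both sides of treatment start, a test after the amendment of 21 June 2019 falls outside it for anyone who started treatment before about late December 2017.

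The drafting cost is a few sentences and no new data item. Section 7.1 already provides reimbursement for RET tests on available samples done solely to confirm eligibility. The real cost is that some retrospective patients may no longer count towards a target that is already hard to reach.
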